7.2 Medical History and Prior and Concomitant Medications

Medical history data will be coded using the Medical Dictionary for Regulatory Activities (MedDRA). The actual version of the MedDRA coding dictionary will be noted in the statistical tables and clinical study report. The number and percentage of subjects in each medical history category (by MedDRA system organ class (SOC) and preferred term) will be summarized for the ITT Population. The SOC will be presented in alphabetical order, and the preferred terms will be presented in alphabetical order within each SOC. Subjects reporting more than one condition/diagnosis will be counted only once in each row (SOC or preferred term).

Prior and concomitant medications will be summarized separately. A prior medication is defined as any medication taken prior to the date of the first dose of study drug. A concomitant medication is defined as any medication that started prior to the date of the first dose of study drug and continued to be taken after the first dose of study drug or any medication that started on or after the date of the first dose of study drug, but not after the date of the last dose of study drug + 1 day. The number and percentage of subjects taking prior and concomitant medications will be summarized by generic drug name, based on the World Health Organization (WHO) Drug Dictionary. The actual version of the WHO Drug Dictionary will be noted in the statistical tables and clinical study report.

7.3 Protocol Deviations

For each of the following protocol deviation categories and across all categories, the number and percentage of dosed subjects with at least one protocol deviation will be summarized overall and by treatment group:

- Subject entered into the study even though did not satisfy entry criteria;
- Subject developed withdrawal criteria during the study but was not withdrawn;
- Subject received wrong treatment or incorrect dose of study treatment;
- Subject took prohibited concomitant medication.

8.0 Handling of Potential Intercurrent Events for the Primary and Secondary Endpoints

The primary and secondary efficacy endpoints (defined in Section 3.1 and Section 3.2) will be analyzed based on the ITT Population and the following methods will be used to address potential intercurrent events.

Intercurrent events (ICE):

ICE1: Premature discontinuation of study treatment

A treatment policy strategy will be used to handle ICE1, namely, available data collected will be used regardless of premature discontinuation of study treatment.

ICE2: Initiation or dose escalation of UC-related corticosteroid (defined as below) or initiation of any TIM therapy (including biologics and non-biologics) for UC. A composite strategy will be used to handle ICE2, namely, subjects will be considered as not achieving response at or after ICE2.

UC-related corticosteroid ICE is defined as:

- Subjects who were not on UC-related corticosteroids (systemic or locally acting corticosteroids for UC) at Baseline initiate UC-related corticosteroids during the study.
- Subjects who were on UC-related systemic corticosteroids at Baseline who have dosage increased to greater than the prednisone equivalent dose of corticosteroid taken at Baseline, or initiation of any rectal corticosteroids during the study regardless of rectal corticosteroid dose.

The time of ICE2 is defined as the date when either of the two scenarios above first occurs for a subject. As such, the subject will be considered as a "non-responder" for the efficacy endpoint on or after the date of ICE2 through the end of the study. In the scenario when both ICE1 and ICE2 occur, data will be used on or after the date of ICE1 until ICE2, which the subject will be considered as a "non-responder" for the efficacy endpoint on or after the date of ICE2.

Same intercurrent events handling approaches will be used for additional efficacy endpoints, except for:

- For continuous endpoints, data collected on or after ICE2 will be excluded from the analysis (i.e., treated as missing data) handled by mixed effect model repeat measurement (MMRM).
- For time-to-event endpoint, subjects will be censored at ICE2.

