5.3 Prohibited Medications and Therapy

During the study, the following are prohibited medications:

- All biologics or small molecule medication (e.g., JAK inhibitors, sphingosine-1-phosphate [S1P] receptor modulators) with potential impact on UC;
- Initiation of oral aminosalicylates, immunomodulators, IV or oral corticosteroids, and/or UC-related antibiotics;
- Oral or systemic cyclosporine, tacrolimus, or mycophenolate mofetil;
- Rectal therapy with any therapeutic enemas or suppositories, with the exception of those required for endoscopy;
- Parenteral nutrition;
- Fecal microbial transplant;
- Live replicating vaccines are not permitted (non-replicating live viral vaccines such as the Jynneos vaccine can be administered) during study participation and including up to 30 days after the last dose of study drug. Examples of live attenuated vaccines include, but are not limited to, the following:
 - Bacille Calmette-Guérin (BCG)
 - Zoster vaccine live (Zostavax®)
 - Measles-mumps-rubella or measles mumps rubella varicella
 - Monovalent live attenuated influenza A (intranasal)
 - Oral polio vaccine
 - Rotavirus
 - Seasonal trivalent live attenuated influenza (intranasal)
 - Smallpox
 - Monkeypox
 - Oral typhoid vaccine
 - Varicella (chicken pox)
 - Yellow fever
 - Dengue (Dengvaxia®)
- Any known CYP3A inhibitors (e.g., amiodarone, clarithromycin, fluconazole, ciprofloxacin, itraconazole, ketoconazole, quinidine, fluoxetine, and paroxetine) or inducers (e.g., carbamazepine, rifampin, phenobarbital, and phenytoin) of drug metabolizing enzymes within 30 days of the first dose of study drug and through the end of the study.
- Any investigational agent.

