7.3 Handling Potential Intercurrent Events for the Primary and Secondary Endpoints

For both the primary and secondary endpoints, data collected will be used regardless of premature discontinuation of study drug. Subjects will be considered as non-responders after the start of rescue medication (initiation or dose escalation of UC-related corticosteroids).

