3.14 Subject Withdrawal

All attempts must be made to determine the date of the last study drug dose and the primary reason for discontinuation of study drug or study participation. The information will be recorded on the appropriate eCRF page. However, these procedures should not interfere with the initiation of any new treatments or therapeutic modalities that the investigator feels are necessary to treat the subject's condition. Following discontinuation of study drug, the subject will be treated in accordance with the

investigator's best clinical judgment, irrespective of whether the subject decides to continue participation in the study.

In the event a subject withdraws consent from the clinical study, biomarker research will continue unless the subject explicitly requests analysis to be stopped. When AbbVie is informed the subject has withdrawn and no longer wishes biomarker research to continue, samples will not be analyzed, no new biomarker analysis data will be collected for the withdrawn subject or added to the existing data or database(s), and the samples will be destroyed. A subject may withdraw consent for optional biomarker research at any time and remain in the clinical study. Data generated from clinical study and/or optional biomarker research, before subject withdrawal of consent, will remain part of the study results.

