9.2 Handling of Missing Data

9.2.1 Categorical Endpoints

For binary efficacy endpoints, the primary approach to handle missing data will be non-responder imputation (NRI). The NRI approach categorizes any subject who does not have an evaluation during a pre-specified visit window as a non-responder for the visit.

In cases data missing at random can be reasonably assumed (e.g., missing due to pandemic or geo-political reasons), NRI while incorporating multiple imputation (NRI-MI) may be performed as additional approach.

In addition, AO analysis will be performed. The AO analysis will not impute values for missing observations, and thus a subject who does not have an evaluation on a scheduled

visit will be excluded from the AO analysis for that visit. All observed data will be used in AO analysis.

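### SAP 8.0 scores non-response only after corticosteroid or TIM rescue, so a subject who starts another UC therapy the protocol prohibits can still count as an ABBV-668 responder

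*SAP*

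**What the plan says.** **SAP 8.0** names two intercurrent events. ICE1 is stopping study drug early. It is handled by treatment policy: "available data collected will be used regardless of premature discontinuation of study treatment". ICE2 is "Initiation or dose escalation of UC-related corticosteroid (defined as below) or initiation of any TIM therapy (including biologics and non-biologics) for UC". It is handled by a composite strategy, so the subject is a non-responder from that date. The corticosteroid part is then defined in two bullets, and the next sentence reads: "The time of ICE2 is defined as the date when either of the two scenarios above first occurs for a subject".

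**Protocol 3.1 and 7.3** are narrower and name corticosteroids only: "Subjects will be considered as non-responders after the start of rescue medication (initiation or dose escalation of UC-related corticosteroids".

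**Protocol 5.3** prohibits more than ICE2 covers. Its list includes "Initiation of oral aminosalicylates, immunomodulators, IV or oral corticosteroids, and/or UC-related antibiotics" and "Oral or systemic cyclosporine, tacrolimus, or mycophenolate mofetil", therapeutic enemas and suppositories other than those needed for endoscopy, and fecal transplant. Protocol 5.4 adds dose increases of the oral background drugs.

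**After study drug is stopped**, protocol 5.6 keeps subjects on all scheduled visits. Operations Manual 3.14 leaves treatment to the investigator's judgment, "irrespective of whether the subject decides to continue participation in the study".

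**SAP 9.2.1**, on the as-observed (AO) analysis, says: "All observed data will be used in AO analysis".

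**The concern.** The composite strategy for ICE2 exists so that improvement produced by another UC treatment is not credited to ABBV-668. The SAP widened the protocol's rule from corticosteroids to TIM, which accepts that principle, but it stops there without giving a reason. The same logic applies to the other UC therapies in protocol 5.3 and 5.4. Under ICE2 as written, their use leaves response status unchanged.

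The trial has no concurrent control arm. The comparator is a fixed prior built from historical placebo data, so nothing within the study offsets a response that came from another therapy. At stake are the primary endpoint and the four secondary endpoints, each judged on 40 subjects.

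**Working it through.** **1. Is the gap in the text?**

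| Therapy restricted in protocol 5.3/5.4 | In ICE2? |
|---|---|
| Corticosteroids (IV, oral, rectal) | Yes |
| Biologics and targeted small molecules | Yes, as TIM |
| Oral aminosalicylates, start or increase | No |
| Immunomodulators, start or increase | No |
| Cyclosporine, tacrolimus, mycophenolate | No |
| UC-related antibiotics, start or increase | No |
| Rectal therapy other than corticosteroid | No |
| Fecal transplant | No |

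TIM cannot be read to absorb the last six rows. Eligibility criterion 23 lists aminosalicylates, immunosuppressants and TIM as separate classes, and its TIM agents are biologics, JAK inhibitors and ozanimod.

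**2. Can such a subject reach Week 8 as a responder?**
- After stopping drug: scheduled visits continue (protocol 5.6), new treatment is allowed (Operations Manual 3.14), a Week 8 endoscopy is expected for anyone in the study through Week 6 (Operations Manual 3.16), and ICE1 uses the result as observed.
- On drug: prohibited medication is a withdrawal reason only where continuing study drug would put the subject at risk (protocol 5.5). SAP 7.3 counts it as a deviation, with no effect on response.
- No planned analysis closes the path. NRI and NRI-MI act on missing evaluations, and AO uses what was observed.

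**3. The plan's own figure.** Inputs from SAP 2.4: N = 40, treatment prior Beta(0.5, 0.5), effect +30 points, criterion Pr(difference > 0) > 0.90. With x responders the treatment posterior is Beta(0.5 + x, 40.5 − x). Let r be the smallest x that meets the criterion. The probability of success is then Pr(X ≥ r), X ~ Binomial(40, p0 + 0.30). The primary placebo prior is redacted, so I assumed rates p0 from 3% to 25% and prior sizes from 60 to 560, close to the range of sizes in Table D-1. Success probability runs from 0.991 to 1.000, so the stated figure of more than 90% reproduces. It does not depend on the ICE2 definition.

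**4. What one subject is worth.** The observed rate moves by 1/40 = 2.5 points and the posterior mean by 1/41 = 2.4 points. Pr(difference > 0) on either side of the 0.90 level:

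| Endpoint and placebo prior | One fewer responder | At r |
|---|---|---|
| Clinical remission, Beta(14.0, 312.4), printed | 3/40: 0.837 | 4/40: 0.938 |
| Endoscopic remission, Beta(9.0, 547.8), printed | 1/40: 0.732 | 2/40: 0.931 |
| Primary, assumed 8%, size 300: Beta(24, 276) | 5/40: 0.841 | 6/40: 0.927 |
| Primary, assumed 10%, size 300: Beta(30, 270) | 6/40: 0.842 | 7/40: 0.922 |
| Primary, assumed 8%, size 60: Beta(4.8, 55.2) | 6/40: 0.890 | 7/40: 0.940 |

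Over the assumed range r lies between 3 and 15, so where the boundary falls for the primary endpoint cannot be known from the documents.

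**5. How often would one subject matter?** Take p0 = 10% and prior size 300, where r = 7.
- Under the planned effect about 40 × 0.40 = 16 respond. Removing one leaves 15/40, with posterior above 0.999. The chance of landing exactly on 7 is C(40,7) × 0.40^7 × 0.60^33 = 0.0015, about 0.1%.
- If the drug equals placebo, the chance of landing exactly on 7 is C(40,7) × 0.10^7 × 0.90^33 = 0.058, about 6%.
- If the drug equals placebo, Pr(X ≥ 7) is 0.0995. It would be 0.228 if other therapies added 2.5 points, and 0.393 if they added 5 points. Both increments are assumptions, and both suppose that the historical rate contains no such contribution.

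**The case against.** Several points on the other side have force.

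- **Estimand choice.** The protocol reserves the term rescue medication for corticosteroids, and a sponsor may leave other therapies under treatment policy. This stands in principle. But the SAP has already gone beyond the protocol by adding TIM, and neither document says why the line falls there.
- **Direction.** A reader might infer that the bias can only favour ABBV-668. The documents do not support that. Historical placebo subjects may have started the same therapies. If those trials also scored only corticosteroid or TIM use as non-response, the placebo rate carries a similar contribution, and widening ICE2 on one side alone would create a mismatch against the drug. This stands, and it shapes the fix.
- **Limited opportunity by Week 8.** These starts are prohibited through Week 16. Criterion 23 uses 90 days for thiopurines and methotrexate, and 4 weeks for aminosalicylates, before calling a treatment failed. The endpoint is centrally read. This narrows the path without closing it.
- **TIM date.** Because the ICE2 date sentence follows the two corticosteroid bullets, a reader might infer that a TIM start has no ICE2 date. SAP 2.1 and Tables 1 and 2 include TIM in the estimand and in ICE2, so the intent is clear. Only the sentence needs repair.
- **AO analysis.** A reader might infer that AO counts responses after ICE2. The sentence sits in the missing-data section, and SAP 8.0 makes no exception for AO. It is ambiguous, and for the primary and secondary endpoints AO is only a sensitivity analysis.
- **The 0.90 level.** It appears only in the sample-size text. SAP 9.3.2 calculates and reports the posterior probability and sets no success rule, so crossing 0.90 is not a formal change of outcome.

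**Conclusion.** The concern holds as a gap in the ICE2 definition. Starting a UC therapy that protocol 5.3 or 5.4 prohibits, other than a corticosteroid or TIM, leaves a subject eligible to count as a responder in every planned analysis.

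The likely direction is in favour of ABBV-668, but this is not established while the historical scoring rule is unstated. The size is unknown, because the documents give no rate for such starts, and corticosteroids and TIM may cover most rescue. Each affected subject is worth 2.5 points. That could matter for a drug with little effect, where the count may fall near the 90% level. It would not change the conclusion at the planned 30-point effect. The clinical remission and endoscopic remission figures rest on priors printed in Table D-1. Those for the primary endpoint rest on assumed priors.

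This is worth correcting because the correction is cheap. It does not show that the primary result would be wrong.

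**What to change.** These changes concern analysis only. No treatment rule changes.

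1. Pre-specify an analysis of the primary and secondary endpoints with ICE2 widened to the start, or increase above the Baseline dose, of any UC therapy prohibited in protocol 5.3 or 5.4. Date these events from all medication records through the 30-Day Follow-Up. Do not use the concomitant-medication definition in SAP 7.2, which excludes anything started later than one day after the last dose.
2. Establish how the historical placebo trials scored these therapies. If they were scored the same way, or can be, make the wider rule primary. Otherwise report it as a sensitivity analysis beside the SAP version 3.0 definition.
3. Reword the ICE2 date as the earliest of any corticosteroid event or TIM start.
4. State that ICE2 non-response also applies in the AO analysis, so that AO drops only missing evaluations.
5. Align protocol 3.1 and 7.3, which name corticosteroids only, with SAP 2.1 and 8.0.

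The cost is a SAP revision, matching protocol wording, and a check of the historical data. Protocol 5.4 already has medications recorded through the 30-Day Follow-Up. The downside is that the observed response rate may be slightly lower.

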3 OBJECTIVE AND ENDPOINTS

3.1 Objective, Hypothesis, and Estimands

Primary

To characterize the safety and efficacy of ABBV-668 CCI mg orally (PO) twice a day (BID) as treatment in adult subjects with moderately to severely active UC.

Hypothesis

The primary hypothesis is that ABBV-668 will be safe, well tolerated and efficacious in subjects with moderate to severe UC.

Estimands

The estimand for the primary endpoint is defined as the difference in the proportion of subjects achieving endoscopic improvement at Week 8 regardless of premature discontinuation of study treatment and without initiation or dose escalation of UC-related corticosteroids between the ABBV-668 treatment group in the Intent-to-Treat (ITT) Population and the historical placebo group. Subjects will be counted as non-responders after the start of rescue medication (initiation or dose escalation of UC-related corticosteroids).

The estimands corresponding to the secondary efficacy objectives are:

For each binary secondary endpoint specified in Section 3.3: The difference in the proportion of subjects achieving a response regardless of premature discontinuation of study treatment and without initiation or dose escalation of UC-related corticosteroids in the ABBV-668 treatment group in the ITT Population versus in the historical placebo group. Subjects will be counted as non-responders after the start of rescue medication (initiation or dose escalation of UC-related corticosteroids).

Definitions of Efficacy Endpoints

Clinical Remission per Adapted Mayo Score: stool frequency subscore (SFS) ≤ 1 , and not greater than Baseline, rectal bleeding subscore (RBS) = 0, and endoscopic subscore (ESS) ≤ 1

Clinical Response per Adapted Mayo Score: decrease from Baseline ≥ 2 points and $\geq 30\%$, PLUS a decrease in RBS ≥ 1 or an absolute RBS ≤ 1

Clinical Response per Partial Adapted Mayo Score: decrease from Baseline ≥ 1 points and $\geq 30\%$, PLUS a decrease in RBS ≥ 1 or an absolute RBS ≤ 1

Clinical Remission per Full Mayo Score: Full Mayo score ≤ 2 with no subscore > 1

Clinical Response per Full Mayo Score: decrease from Baseline ≥ 3 points and $\geq 30\%$, PLUS a decrease in RBS ≥ 1 or an absolute RBS ≤ 1

Endoscopic Improvement: Mayo ESS of 0 or 1. Note that evidence of friability during endoscopy in subjects with a Mayo ESS of 0 or 1 will confer an endoscopic subscore of 2.

Endoscopic Remission: Mayo ESS = 0

Histologic Remission: Geboes score of < 2.0

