✓ 21. No history of dysplasia of the gastrointestinal tract or evidence of dysplasia in any biopsy performed during the Screening endoscopy, other than completely removed low-grade dysplastic lesions (historically or during Screening).

✓ 22. No history of lymphoproliferative disease, including lymphoma, or signs and symptoms suggestive of possible lymphoproliferative disease, such as lymphadenopathy and/or splenomegaly.

Prior and Concomitant Medications

✓ 23. Subject must have demonstrated an inadequate response to, loss of response to, or intolerance to at least one of the following: oral aminosalicylates, corticosteroids, immunosuppressants, and/or targeted immunomodulators (including biologics and non-biologics) as defined below:

Note: Intolerance does not require minimum dose or duration of use.

- Oral aminosalicylates (e.g., mesalamine, sulfasalazine, olsalazine, balsalazide)
 - Signs and symptoms of persistently active disease, in the opinion of the investigator, during a current or prior course of at least 4 weeks of treatment with 2.4 g/day mesalamine (2 g/day if controlled release), 4 g/day sulfasalazine, 1 g/day olsalazine, or 6.75 g/day balsalazide.

- Corticosteroids
 - Signs and symptoms of persistently active disease despite a history of at least one induction regimen that included a dose equivalent to prednisone \geq 40 mg/day PO for at least 3 weeks or intravenously for 1 week, OR
 - Unable to taper corticosteroids to below a dose equivalent to prednisone 10 mg daily PO without recurrent active disease, OR
 - Signs and symptoms of persistently active disease during or after a course of at least 4 weeks of treatment with 9 mg/day budesonide or 5 mg/day beclomethasone, OR
 - Unable to taper oral budesonide to at or below 6 mg/day without recurrent active disease, OR
 - History of intolerance to corticosteroids (including, but not limited to Cushing's syndrome, osteopenia/osteoporosis, hyperglycemia, insomnia, infection).
- Immunosuppressants

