2.0 Study Objectives and Design

2.1 Study Objectives

The primary efficacy objective of the study is to demonstrate greater proportion of subjects achieving endoscopic improvement with ABBV-668 treatment in the Intent-to-Treat (ITT) Population, which consists of all enrolled subjects with at least one dose of study treatment, when compared with historical placebo group.

The hypothesis corresponding to the primary efficacy objective is that the proportion of subjects achieving endoscopic improvement with ABBV-668 treatment at Week 8 is greater than the historical placebo group. The estimand for the primary endpoint is defined as the difference in the proportion of subjects achieving endoscopic improvement at Week 8 without initiation or dose escalation of UC-related corticosteroids and without initiation of any targeted immunomodulators (TIM) therapy (including biologics and

non-biologics), regardless of premature discontinuation of study treatment, between the ABBV-668 treatment group in the ITT Population and the historical placebo group.

The secondary efficacy objectives are to evaluate the efficacy of ABBV-668 with respect to the secondary endpoints specified in Section 3.2.

The estimands corresponding to the secondary efficacy objectives are:

For each binary secondary endpoint specified in Section 3.2: The difference in the proportion of subjects achieving a response without initiation or dose escalation of UC-related corticosteroids and without initiation of any TIM therapy (including biologics and non-biologics), regardless of premature discontinuation of study treatment, between the ABBV-668 treatment group in the ITT Population and the historical placebo group.

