9.3.2 Main Analysis of Primary Efficacy Endpoint(s)

Analysis of the primary efficacy endpoint will be conducted on the ITT Population. Comparison of the primary efficacy endpoint will be performed between the ABBV-668 treatment group and historical placebo group using Bayesian approach with prior distribution **CCI** obtained from meta-analysis for the historical placebo data, and non-informative prior *Beta* (0.5, 0.5) for the ABBV-668 treatment group. The posterior probability of rate difference > 0 given data will be calculated. The mean difference and the corresponding 95% credible interval will be provided. Point estimate and 95% CI using normal approximation will be provided for the response rate for the ABBV-668 group. Plots of prior and posterior distribution for the rate difference between ABBV-668 and historical placebo will also be provided.

The attributes of the estimand corresponding to the primary efficacy endpoint are summarized in Table 1.

Table 1. Summary of the Estimand Attributes Corresponding to the Primary Efficacy Endpoint

Estimand Label	Attributes of the Estimand					Statistical Summary
	Treatment	Endpoint	Population	Handling of Intercurrent Events		
Primary: Achievement of endoscopic improvement at Week 8 vs. Historical Placebo	ABBV-668	Achievement of endoscopic improvement at Week 8	Adult subjects with moderately to severely active UC	ICE1: Premature discontinuation of study treatment (treatment policy) ICE2: Initiation or dose escalation of UC-related corticosteroids or initiation of any TIM therapy (composite) All data will be used regardless of ICE1 occurrence. Subjects will be considered as non-responders on or after the date of ICE2.	ICE1: Premature discontinuation of study treatment (treatment policy) ICE2: Initiation or dose escalation of UC-related corticosteroids or initiation of any TIM therapy (composite) All data will be used regardless of ICE1 occurrence. Subjects will be considered as non-responders on or after the date of ICE2.	Difference in proportion of subjects achieving response

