9.4.2 Analyses of Secondary Efficacy Endpoints

Point estimate and 95% CI using normal approximation will be provided for the response rate for ABBV-668 treatment group. The same Bayesian approach specified in Section 9.3.2 will be also conducted based on the ITT Population, if applicable.

The attributes of the estimands corresponding to the secondary efficacy endpoints are summarized in Table 2.

Table 2. Summary of the Estimand Attributes Corresponding to the Secondary Efficacy Endpoints

Estimand Label	Attributes of the Estimand					Statistical Summary
	Treatment	Endpoint	Population	Handling of Intercurrent Events		
Binary Secondary Variable	ABBV-668 vs. Historical Placebo	Achievement of each binary secondary endpoint respectively	Adult subjects with moderately to severely active UC	ICE1: Premature discontinuation of study treatment (treatment policy) ICE2: Initiation or dose escalation of UC-related corticosteroids or initiation of any TIM therapy for UC (composite) All data will be used regardless of ICE1 occurrence. Subjects will be considered as non-responders on or after the date of ICE2.		Difference in proportion of subjects achieving response

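### The corticosteroid intercurrent event in SAP 8.0 misses a subject whose only UC corticosteroid at Baseline is locally acting, so it does not fully implement the estimand

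*SAP*

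**What the plan says.** The estimand is broad. SAP 2.1 defines response as achieved "without initiation or dose escalation of UC-related corticosteroids and without initiation of any targeted immunomodulators (TIM) therapy". Protocol 3.1 and 7.3 likewise make initiation or dose escalation of UC-related corticosteroids a non-response, and Tables 1 and 2 of the SAP (9.3.2 and 9.4.2) repeat the wording. None of these separates systemic from locally acting drugs.

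SAP 8.0 names the same event as ICE2 but states that its corticosteroid part is defined by two bullets:

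- Limb 1: "Subjects who were not on UC-related corticosteroids (systemic or locally acting corticosteroids for UC) at Baseline initiate UC-related corticosteroids during the study".
- Limb 2: "Subjects who were on UC-related systemic corticosteroids at Baseline who have dosage increased to greater than the prednisone equivalent dose" taken at Baseline, or who start any rectal corticosteroid.

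ICE2 is dated by the first occurrence of either of two scenarios. Under ICE1, data after stopping study drug are kept until ICE2 occurs.

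**The concern.** Limb 1 counts locally acting drugs as UC corticosteroids at Baseline, so a subject taking one is outside that limb. Limb 2 admits only subjects on a systemic one. A subject on a locally acting drug alone falls between them, and a later increase in that drug or a start of a systemic corticosteroid is not flagged. Programming from the bullets would analyse that subject's Week 8 data as observed.

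For binary endpoints this can only raise the observed ABBV-668 rate. The effect on the difference from historical placebo also depends on how corticosteroid rescue was counted in the historical trials, which the documents do not show. No direction is claimed for continuous endpoints.

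**Working it through.** **Step 1. Baseline state against on-study event, under the two limbs and under the estimand**

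| UC corticosteroid at Baseline | On-study event | SAP 8.0 limbs | Estimand |
|---|---|---|---|
| None | Any UC corticosteroid started | Limb 1 | Non-response |
| Systemic | Above Baseline prednisone-equivalent dose, or rectal start | Limb 2 | Non-response |
| Locally acting only | That drug increased | Neither | Non-response |
| Locally acting only | Systemic drug started | Neither | Non-response |
| Locally acting only | Rectal drug started | Neither, unless the rectal clause is read as applying to everyone | Non-response |

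**Step 2. Can the group exist?** The documents do not say which drugs are locally acting, so there are three cases.

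- (a) Oral budesonide or beclomethasone is locally acting (an inference). Criterion 28 in Protocol 5.1 admits both up to a cap, so the gap is real.
- (b) Only rectal drugs are locally acting. Criterion 30 bars rectal corticosteroids from 14 days before the Screening endoscopy through the rest of Screening, so the group is essentially empty.
- (c) Oral budesonide and beclomethasone are coded as systemic. Limb 2 then catches added prednisone or an IV corticosteroid. Only an increase in the drug itself stays open: limb 2 works in prednisone equivalents, criteria 23 and 28 give these drugs in their own mg/day (for example "at least 4 weeks of treatment with 9 mg/day budesonide or 5 mg/day beclomethasone"), and no conversion is stated.

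**Step 3. How could the event arise?** Protocol 5.3 and 5.4 prohibit these changes, so on treatment they would be deviations. The other route is a subject who stops study drug, stays in the study on standard of care (Protocol 5.6 and 6.2) under the investigator's judgment (Operations Manual 3.14), and has the Week 8 endoscopy expected of anyone still in the study through Week 6 (Operations Manual 3.16).

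**Step 4. Size per subject** (n = 40; treatment prior Beta(0.5, 0.5), SAP 2.4)

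- Observed rate: 1/40 = 2.5 points.
- Posterior mean (x + 0.5)/41: 1/41 = 2.4 points.
- For comparison, the Wald 95% half-width 1.96 × √(p(1 − p)/40) is 14.5, 14.8, 15.0 and 15.2 points at x = 13, 14, 15 and 16.

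**Step 5. How many subjects?** The documents give no figures, so these inputs are assumptions: 2 to 8 of 40 on such a drug alone, 10% to 25% of them escalated by Week 8, 10% to 40% of those meeting the criterion.

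- Empty group: 0.
- Low: 2 × 0.10 × 0.10 = 0.02 responders (0.05 points); chance of at least one 1 − 0.99² = 0.02.
- High: 8 × 0.25 × 0.40 = 0.8 responders (2.0 points); chance of at least one 1 − 0.90⁸ = 0.57.

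**Step 6. Does one such responder change the conclusion?** The quantity is P(p_drug > p_placebo), with p_drug ~ Beta(x + 0.5, 40 − x + 0.5), by numerical integration. The primary placebo prior is redacted, so Beta(r·e, (1 − r)·e) is assumed. The larger count is about r + 30 points; the smaller removes one responder.

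| Endpoint and prior | Responders | Without | With |
|---|---|---|---|
| Primary, r = 5%, e = 60 | 13, 14 | 0.99994 | 0.99998 |
| Primary, r = 8%, e = 60 | 14, 15 | 0.99976 | 0.99991 |
| Primary, r = 11%, e = 60 | 15, 16 | 0.99938 | 0.99974 |
| Clinical remission, Beta(14.0, 312.4) | 13, 14 | 1.0000 | 1.0000 |
| Clinical response, Beta(85.7, 241.0) | 21, 22 | 0.9996 | 0.9999 |
| Partial Adapted Mayo response, Beta(20.9, 38.4) | 25, 26 | 0.9965 | 0.9984 |
| Endoscopic remission, Beta(9.0, 547.8) | 12, 13 | 1.0000 | 1.0000 |

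With e = 560 the primary values are 0.99999 or higher throughout. The secondary priors are those in SAP Table D-1.

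A weaker result is more sensitive. With an assumed prior of mean 8% and size 300, going from 5 to 6 responders moves the probability from 0.841 to 0.927, across the 90% level used in the sample-size statement. The plan does not state 90% as a formal decision rule.

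**The case against.** The strongest reply is that the split is by route: locally acting means rectal, the only local form SAP 8.0 names, and the protocol lists oral budesonide and beclomethasone with prednisone as oral corticosteroids. Criterion 30 then leaves no eligible subject between the limbs. That reading is possible. But under it, limb 1's mention of locally acting drugs at Baseline would have almost no content, and criterion 28 caps budesonide and beclomethasone separately from prednisone or equivalent.

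A second reply is that the ICE2 heading, SAP 2.1 and the estimand tables all state the broad rule, so this is a drafting gap and not a changed estimand. That is fair as to intent, but the heading refers to the bullets for its definition.

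Third, on-treatment escalation is prohibited and would be summarised as a deviation (SAP 7.3), and starting a targeted immunomodulator for UC already triggers ICE2. These points narrow the route to subjects escalated by corticosteroid alone before Week 8. They do not close it, since a deviation listing does not alter responder status.

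Fourth, the upper figure of 0.8 responders sets three undocumented inputs to their maximum at once. It is a bound under assumptions and not an expectation.

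**Conclusion.** The concern holds and is minor. As written, the two limbs leave out a Baseline state that limb 1 itself recognises, so the rule does not fully implement the estimand. That rests on the wording alone. The practical size rests on how oral budesonide and beclomethasone are classed and on how many subjects are escalated. It is probably small and possibly zero. One misclassified responder would not alter the conclusion at the planned effect: the primary probability stays at or above 0.9993 for the placebo priors assumed, and the secondary probabilities at or above 0.9965 for the Table D-1 priors. It could matter only if the result lay near the 90% level.

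**What to change.** In SAP 8.0, as an analysis definition only:

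- Keep limb 2's prednisone-equivalent test for subjects on systemic corticosteroids at Baseline.
- Add a limb for subjects on only locally acting UC corticosteroids at Baseline. ICE2 occurs at the first increase above the Baseline dose of that drug, or at the start of any other UC-related corticosteroid (oral, IV or rectal), including a switch to a systemic one.
- State that rectal initiation counts for every subject.
- List which drugs are coded as systemic and which as locally acting, and say how escalation is judged for drugs outside the prednisone-equivalent scale.

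The cost is one limb, a short drug list and an update to the ICE derivation. No new data are needed, because Protocol 5.4 already has medication recorded through the 30-Day Follow-Up Visit. The observed response rate may come out slightly lower. Patient care is unchanged.
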